### Three-minute Step Test

The procedure for completing the 3-minute step test is as follows. All participants will be fitted with a chest-worn heart rate monitor (Polar, Finland) that will be used for real-time monitoring by trained EPARC staff throughout all of testing. Participants will then be instructed to step up and down from a single step 8 inches in height at a rate of 24 steps per minute for 3 minutes. The cadence of stepping will be monitored by trained EPARC staff. Upon completion of the test, participants will be asked to sit in a chair and rest.

### Psychological Measures

- The **Rosenberg Self-Esteem Scale**, a well-established 10-item questionnaire, will assess self-esteem. items concerning positive and negative feelings about the self (e.g., “On the whole, I am satisfied with myself.”). Agreement with an item is evaluated on a 4-point response scale, ranging from “strongly disagree” to “strongly agree”.
- Body image will be assessed with the body dissatisfaction subscale of the **Eating Disorder Inventory (EDI)**. This 9-item scale reflects the belief that specific parts of the body associated with increased ‘fatness’ are too large (e.g., hips, thighs, buttocks) (e.g., “I think my stomach is too large.”). Items are evaluated on a 6-point response scale, ranging from “never” to “always”.
- Depression will be measured with the short form of the **Center for Epidemiologic Studies Depression Scale**, which consists of 10 items designed to assess depression in the general population (e.g., “I felt depressed.”). Items are evaluated on a 4-point response scale, ranging from “rarely or none of the time” to “most or all of the time”.
- **Anxiety** will be measured using the short-form of the state scale of the **Spielberger State Trait Anxiety Inventory (STAI)**, which consists of 6 items that comprise the most highly correlated anxiety-present and anxiety-absent items from the full-form of the STAI (e.g., “I feel calm.”). Items are evaluated on a 4-point response scale, ranging from “not at all” to “very much”.
- **Social Support** will be measured using the **Social Support and Eating Habits Survey** and the **Social Support and Exercise Survey**. The surveys consist of items that assess the level of support individuals making changes to their eating habits and exercise are receiving from their family and friends.

### Other Measures

- Homelessness will be assessed at each measurement visit after baseline with item A6 of the **RAND Homelessness Survey**. This item asks respondents to recall how many nights in the past week they spent in a non-permanent residence (e.g., shelter, car/vehicle, etc.)

### Social Media and Network Connectivity Measures

We will collect participants’ Facebook, Twitter and Instagram data via the application programming interfaces of the respective platforms, if possible according to the rules and regulations of the platforms. We have done this in previous studies, while successfully maintaining participants’ privacy and complying with

requirements from the UCSD institutional review board. These data will allow us to measure the frequency and composition of participants' online communication about healthy-active-living (HAL). Broadcasted posts (e.g., a status update or tweet) that include text will be classified with a dictionary consisting of PA (e.g., swimming) and diet (e.g., fruits) unigrams that was developed by Drs. [name] and [name].

Existing and study-engineered online social network connections (e.g., friends and followers) will be tracked, which will allow for the generation of a number of social network statistics that describe the local structural features (e.g., centrality, tie strength, transitivity) that previous research suggests could be important for health behavior change.

Closest social network connections will be measured by asking participants to name up to 10 of their closest friends regardless of whether they are connected online and respond to 5 questions about the friendship (e.g., "How often do you interact with the friend in real life?"). This measure will be used to determine how real world tie strength may be inferred from easily quantifiable online social network interactions.

#### Engagement with Intervention Modalities

We acknowledge that the measurement of engagement in the era of digital health is difficult, and throughout the proposed research, we will keep abreast of state-of-the-science methods to accomplish this. Among intervention group participants, quantitative markers of engagement will include usage of Fitbit, SMS sent and replied to, interactions on Facebook and Twitter related to study content (e.g., a post or tweet, like or favorite), website log-ins and click-throughs, emails sent and replied to, and communication with the health coach.

Because this approach does not take into account the depth of interactions (e.g., liking a post is quantitatively the same as writing a post) nor the common practice of lurking (i.e., passively consuming content but not interacting in a visible way), we will also collect qualitative markers of engagement. A previously used questionnaire that includes eight questions (e.g., "In the past week, on average, approximately how many minutes per day have you spent on Facebook?") meant to measure the intensity with which participants use a device or app will be adapted for use in the present study. Importantly, the qualitative markers of engagement will be measured in both the intervention and control groups. These data, combined with the data from online social network connections, will allow us to explore the influence that contamination (i.e., control participants inevitably will use weight-related devices and apps and be connected to and interact with intervention participants on social media) has on intervention effects.

#### Usability and Acceptability

We will conduct audio recorded exit interviews of intervention participants to gain an understanding of which modalities, content areas, SWMs, and BCTs were used and how the overall user experience of the intervention was perceived. Our approach will be similar to that used in the SMART study.

**Table 7. List of measures and assessment timepoints**

Measures	Assessment Time Point				
	0	6	12	18	24
Demographic information	X				
Weight, height, waist and arm circumference, blood pressure, heart rate, heart rate variability, PA, sleep, diet, sedentary behavior, strategies for weight management, self-esteem, body image, anxiety, depression, online communication about healthy-active-living, online social network connections, closest social network connections, quantitative and qualitative markers of engagement, contamination	X	X	X	X	X
Other measures (homelessness)		X	X	X	X
Body composition (DXA)	X	X	X	X	X
Three-minute Step Test	X	X	X	X	X

Usability and acceptability					X
Device- and app-based measures of weight, PA, sleep, diet, heart rate will be measured continuously among all participants	→	→	→	→	→

Additionally, the study team may recontact participants following the conclusion of the study to ask additional questions and/or inquire about participation in other research. Participants will indicate whether they agree to be recontacted on the study consent form. Only participants who agree to be recontacted will be contacted by study team and participants will be reconsented.

## **Data Entry and Management**

All measures will be collected and managed using the secure, web-based tool Research Electronic Data Capture (REDCap) hosted at UCSD. REDCap provides an intuitive interface for data entry; audit trails for tracking data manipulation and export procedures; automated export procedures for seamless data downloads to common statistical packages; and procedures for importing data from external sources (e.g., all study anthropometric and physiological measures).

## **Statistical Considerations**

### **Power and Sample Size**

In order to ensure that the RCT has adequate power to determine the efficacy of the SMART 2.0 intervention to improve weight in kg, we calculated the sample size based on a two-sided, two-sample t-test with 80% power at a significance level of 2.5% (a Bonferroni correction to account for two tests). In the SMART study, the standard deviation (SD) of change in weight at 6 and 12 months ranged from 3.87 kg to 5.97 kg, and we have assumed that the corresponding SD in SMART 2.0 will fall within this range. Furthermore, the smallest statistically significant mean difference in change in weight between the two groups occurred at 12 months and was approximately -1.33 kg. If we assume an SD of 4.92 and a modest increase in the between group difference (-1.60 kg), then we will need 182 subjects per group in order to detect a minimal standardized effect size of 0.33. Thus, we will randomize 642 participants (214 per group accounting for a 15% attrition rate).

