**6. SPECIFIC AIMS**

The primary aim of the study is to determine the efficacy of SMART 2.0 with technology and personal health coaching or with technology alone to improve objectively measured weight in kg over 24 months (96 weeks) compared to a control group.

Secondary aims will be to evaluate the following:

1. Anthropometric and physiological outcomes, physical activity, diet, sleep, self-esteem, body image, anxiety, depression, and the frequency and composition of participants' online communication about weight-related behaviors between groups at 6, 12, 18, and 24 months
2. The dose response (i.e., quantified engagement with technological modalities) of the intervention
3. The usability and acceptability of the intervention
4. Potential mediators and moderators of the intervention effects (e.g., social network connectivity, contamination, etc.)
5. Patterns of change in physical activity, diet, and sleep

Given that SMART 2.0 has been greatly enhanced by what we have learned from previous research, we hypothesize that both interventions will significantly improve weight compared to the control group, and the group receiving personal health coaching will experience the greatest improvement. We further hypothesize

that differences in secondary outcomes will favor the SMART 2.0 intervention groups. There is a critical need to advance our understanding of how to develop and deploy multimodal, technology-based weight-loss interventions that have the potential for long-term effects and widespread dissemination among young adults. SMART 2.0 is designed to maximize efficacy in a scalable manner. By measuring usability and acceptability, this study will inform intervention dissemination to campus wellness programs should the findings warrant it.

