(EARLY) trials, a consortium funded by the NHLBI (U01 HL096715; Principal Investigator (PI): [name]; Co-Investigators (Co-Is): [name], [name], [name], and [name]). It was the only RCT in the consortium to integrate mobile and social technologies within the intervention. In SMART, 404 overweight or obese college students (aged 18 to 35 years) from three universities in San Diego, CA were randomized to receive either the intervention (n=202) or general information about health and wellness (control group, n=202). The 2-year intervention was innovative primarily because it 1) was remotely delivered via 6 technological modalities (i.e., mobile apps, text messaging (SMS), Facebook, emails, a website, and brief ad-hoc technology mediated communication with a health coach) and 2) leveraged participants' existing as well as study engineered social networks to remotely deliver theory-based BCTs and evidence-based strategies for weight management (SWMs). The primary outcome was objectively measured weight in kg at 24 months, and differences between groups were evaluated using linear mixed-effects regression. Participants' mean (standard deviation [SD]) age was 22.7 (3.8) years. They were 70% female and 31% Hispanic. Mean (SD) body mass index was 29.0 (2.8) kg/m^2. At 24 months, weight was assessed in 341 (84%) participants, but all 404 were included in analyses. Weight, adjusted for sex, ethnicity, and college, was significantly less in the intervention group compared to the control group at 6 months (1.51%; -1.33 kg difference, 95% confidence interval (CI) = -2.36 to -0.30, p = 0.011) and 12 months (1.57%; -1.33 kg difference, 95% CI = -2.30 to -0.35, p = 0.008). However, differences between groups at 18 months (-0.67 kg difference, 95% CI = -1.69 to 0.35, p = 0.200) and 24 months (-0.79 kg difference, 95% CI = -2.02 to 0.43, p = 0.204) were not significant.

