The ConTxt study was an RCT that assessed the efficacy of a weight loss intervention delivered almost exclusively via SMS (NCI R01 CA138730; PI: [name]; Co-Is: [name] and [name]). The study built upon the success of an earlier 4-month trial of interactive SMS on weight outcomes, and 298 overweight adults (aged 21-60 years) were allocated to one of three conditions: 1) a control condition; 2) SMS only; or 3) SMS+Health Coach (brief monthly phone calls). The SMS interventions offered 1-4 messages/day which were personalized and tailored using baseline SWMs and then reiteratively and interactively using ecological momentary assessment of PA and diet, goal setting and performance, and "like" or "unlike" messaging controls. The primary outcome was objectively measured weight at 12 months, and differences between groups were evaluated using linear mixed-effects regression. Participants were 77% female and 41% Hispanic. At 12 months, weight was assessed in 253 (85%) participants, but all 298 were included in analyses. Compared to the control group, and controlling for baseline body mass index, the SMS only group lost 1.20% more weight (p = 0.214); and the SMS+Health Coach group lost 2.99% more weight (p = 0.003). Importantly, both SMS interventions were well received, and the results indicate that a weight loss intervention delivered via daily

individualized, dynamic, and interactive SMS was most efficacious when messages were combined with brief monthly communication with a health coach.

Given that 1) the interventions in the SMART and ConTxt studies have evidence of short-term efficacy and can be merged because of their similar theory- and evidence-based content (i.e., BCTs and SWMs); and 2) there is evidence that the incorporation of consumer-level devices and apps along with increased social media and social network connectivity will enhance engagement, we believe that the proposed research is a logical, innovative, and important extension of our previous work.

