interval estimates (95% confidence intervals). An intervention effect will be concluded if the p-value for the study group-by-visit interaction contrast in the model at 24 months is statistically significant. Holm's method will be used to adjust the two p-values for multiple comparisons. This approach uses all available data and is robust to data missing at random (MAR). However, two additional approaches may be employed to examine the influence of missing data on the primary outcome analysis (which takes a likelihood-based approach to estimation, but does not directly impute data). First, we will model the probability of missingness as a function of baseline covariates and previous outcomes (using logistic regression). The inverse of the resulting probabilities will serve as propensity scores that will be included in the model of the primary outcome. If data are MAR or the probability of missingness can be fully explained by observable data, this approach produces asymptotically unbiased estimates. Second, in order to allow for the possibility that the MAR assumption may not hold (an assumption that is not empirically testable), we will use pattern mixture models in which the distribution of the primary outcome is assumed to follow a mixture of two distributions: one for those who complete follow-up and another for those who do not. These approaches will allow us to quantify the robustness of the study findings to missing data assumptions.

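### The 80% power for -1.60 kg uses SMART inputs from 6 and 12 months; at the 24-month test that decides the trial, SMART's own interval implies about 65%

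*Combined protocol and SAP*

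**What the plan says.** All references are to the combined protocol and SAP.

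- **Power and Sample Size (section 8), SD.** The source is SMART, where "the standard deviation (SD) of change in weight at 6 and 12 months ranged from 3.87 kg to 5.97 kg". The plan assumes that the SD in SMART 2.0 will lie in that range.
- **Same section, effect.** The starting point is SMART's smallest significant difference, -1.33 kg at 12 months, which is then enlarged: "If we assume an SD of 4.92 and a modest increase in the between group difference (-1.60 kg". A two-sided two-sample t-test at 2.5% with 80% power gives 182 per group. Allowing for 15% attrition gives 214 per group, 642 in total.
- **Overall Approach, primary aim analysis.** An intervention effect is concluded if "the p-value for the study group-by-visit interaction contrast in the model at 24 months is statistically significant". For the two comparisons with control, "Holm's method will be used to adjust the two p-values for multiple comparisons".
- **Specific Aims (section 6).** On the primary outcome, "we hypothesize that both interventions will significantly improve weight compared to the control group".
- **Background and Significance (section 7).** SMART's 24-month result, which favoured the intervention but was not significant, is reported as "0.79 kg difference, 95% CI = -2.02 to 0.43, p = 0.204" (the difference is negative). On follow-up: "At 24 months, weight was assessed in 341 (84%) participants, but all 404 were included in analyses".

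**The concern.** Both inputs to the power calculation come from visits at which the trial will not be decided. The plan says how it picked the 12-month difference among the earlier results. It does not say why 6- and 12-month figures should stand in for 24 months, although SMART's 24-month result is in the same document.

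The visit matters because SMART's interval is clearly wider at 24 months than before. If the spread of weight change is larger there, 182 per group does not give 80% power for -1.60 kg. SMART was significant at 6 and 12 months but not at 18 or 24, so a null 24-month result is a realistic outcome. It would be read as a negative result from a trial with 80% power for -1.60 kg when the power was materially lower.

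**Working it through.** **1. The plan's own figure.** Inputs from Power and Sample Size: difference 1.60 kg, SD (3.87 + 5.97)/2 = 4.92 kg, two-sided alpha 0.025, power 80%. By the noncentral t distribution this needs 182 per group, with power 80.2% at that size. Attrition: 182/0.85 = 214.1, and 3 × 214 = 642. The arithmetic reproduces. The largest SD that still gives 80% power for 1.60 kg with 182 per group is 4.93 kg, so there is no margin.

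**2. SD implied by SMART at 24 months.** Inputs from Background and Significance: 95% CI -2.02 to 0.43, with 341 weighed. An even split between arms (170.5 each) is assumed.

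- SE = (0.43 + 2.02)/(2 × 1.96) = 0.625. Check: 0.79/0.625 = 1.264, two-sided p = 0.206, against 0.204 reported.
- SD = 0.625/√(2/170.5) = 5.77 kg. Rounding of the CI limits allows 5.75 to 5.79.

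The same method on all four SMART intervals, using 341 throughout because the number weighed is given only for 24 months:

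| Visit | 95% CI (kg) | SE | Implied SD (kg) |
|---|---|---|---|
| 6 months | -2.36 to -0.30 | 0.526 | 4.85 |
| 12 months | -2.30 to -0.35 | 0.497 | 4.59 |
| 18 months | -1.69 to 0.35 | 0.520 | 4.81 |
| 24 months | -2.02 to 0.43 | 0.625 | 5.77 |

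The method returns values close to 4.92 at the visits used for sizing, so it does not inflate SDs in general. The 24-month value stands apart.

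**3. Power at 24 months.** With 182 per group, the SE of a difference is 5.77 × √(2/182) = 0.605, and the noncentrality is 1.60/0.605 = 2.65. With 362 degrees of freedom and alpha 0.025:

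| SD (kg) | Power for 1.60 kg |
|---|---|
| 4.92 (plan) | 80% |
| 5.77 (SMART, 24 months) | 65% |
| 5.97 (top of the plan's range) | 62% |

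At SD 5.77 the difference detectable with 80% power is about 1.87 kg. Restoring 80% for 1.60 kg would need 249 analysed per group: 249/0.85 gives 293 randomized per group, 879 in total.

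**4. Choice of N in step 2.** Using all 404 in SMART's model gives SD = 0.625/√(4/404) = 6.28 kg. That figure already carries the loss from missing weights, so it pairs with the 214 randomized per group: power 65.0%, detectable difference 1.88 kg. Pairing it with 182 would count attrition twice; that gives 57%.

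**5. Holm.** The sizing uses Bonferroni, but the analysis uses Holm, which is more powerful. Simulation (1,000,000 draws, 182 per arm, shared control so correlation 0.5, 543 degrees of freedom):

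| Scenario | Each comparison | At least one | Both |
|---|---|---|---|
| Both arms at -1.60 kg, SD 4.92 | 85% | 92% | 78% |
| Both arms at -1.60 kg, SD 5.77 | 71% | 81% | 61% |

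If only one arm works, Holm gives that arm about 66% at SD 5.77.

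**The case against.** The strongest points on the other side are these.

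- **The SD is inferred.** No document states a 24-month SD. The value comes from a SMART mixed model adjusted for sex, ethnicity and college, whereas SMART 2.0 will model change adjusted for baseline weight. Sampling error in the SD (chi-square interval, 339 degrees of freedom) gives 5.37 to 6.24 kg, so power of about 72% to 58% at alpha 2.5%. This stands, and the figures should be read as approximate. The range still does not reach 80%.
- **5.77 kg lies inside the plan's assumed range.** True: 3.87 to 5.97 kg already spans about 95% to 62% power for -1.60 kg. But the plan states one power figure, taken at the midpoint, and the range itself is for 6 and 12 months.
- **The true effect may be larger.** Background reports that at 12 months in the text-messaging trial "the SMS+Health Coach group lost 2.99% more weight (p = 0.003". On SMART's 12-month ratio (1.57% for 1.33 kg), 2.99% is about 2.5 kg, with about 97% power at SD 5.77. This is fair support for the coaching arm, though at 12 months and in another population. The messaging-only arm's 1.20% converts to about 1.0 kg, with about 29% power. The assumption of -1.60 kg is not disputed here; the issue is the power claimed for it.
- **No estimate or decision rule is affected.** Correct. The planned 95% confidence intervals will show the precision achieved, which limits the harm.

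**Conclusion.** The concern holds. The sample size arithmetic is right, but the stated 80% power is not supported for the 24-month test. On SMART's 24-month figures, power for -1.60 kg is about 65% at alpha 2.5% and about 71% per comparison under Holm if both arms achieve that difference. The hypothesis that both arms beat control has about a 61% chance of being confirmed, against 78% at the plan's SD. These figures rest on a back-calculated SD of about 5.8 kg, an even split of the 341 weighed in SMART, 182 evaluable per group, and similar precision from the SMART and SMART 2.0 models. The validity of the primary analysis is not in question. This should be corrected, but it is a correction to a stated assumption and power claim.

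**What to change.** Keep 642 participants and leave the test as it is. In Power and Sample Size:

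1. Replace the 6- and 12-month SD with the SMART SD of weight change at 24 months, from the team's own SMART data if available. Otherwise use about 5.8 kg and label it as back-calculated from the published interval.
2. State one of two things: about 65% power for -1.60 kg at 24 months at alpha 2.5% (about 71% per comparison under Holm if both arms achieve it), or 80% power for about -1.9 kg.
3. Say that -1.60 kg is about twice SMART's 24-month difference (1.60/0.79 = 2.03) and is assumed because the intervention has been enhanced.

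The cost is one reworded paragraph and a less favourable stated power or detectable difference. No participants are added and no analysis changes.
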